- **PFS on next-line of therapy (PFS2)** is defined as the time from randomization to disease progression on next-line of treatment, or death from any cause, (whichever occurs first).
- **Progression-free survival (PFS) by investigator assessment** is defined as the time from the date of randomization to the date of first documentation of disease progression based on the investigator assessment per RECIST v.1.1 or death (whichever occurs first).
- **Model-predicted clearance and AUC** for lenvatinib in Arms A and B.
- **Model-predicted clearance and AUC** for everolimus in Arm A.

Exploratory Endpoints

- **Duration of response (DOR)** is defined as the time from the date a response was first documented until the date of the first documentation of disease progression or date of death from any case.
- **Disease control rate** is the proportion of subjects who have best overall response of CR or PR or SD. Stable disease must be achieved at ≥ 7 weeks after randomization to be considered best overall response.
- **Clinical benefit rate** is the proportion of subjects who have best overall response of CR or PR or durable SD (duration of SD ≥ 23 weeks after randomization).
- **Blood and tumor biomarkers** will be assessed for identifying potential correlation with clinical outcomes-related endpoints.

Analysis Sets

The Full Analysis Set (Intent-to-Treat Analysis [ITT] Population) is the group of all randomized subjects regardless the treatment actually received. This is the primary analysis population used for all efficacy analyses which will be based on the intent-to-treat principle.

The Per Protocol Analysis Set is the group of those subjects who received at least 1 dose of study drug, had no major protocol deviations and had both baseline and at least 1 post-baseline tumor assessments. Subjects for whom death occurred prior to the first post-baseline tumor assessment will also be included. The per protocol analysis set will be the secondary analysis set for efficacy endpoints.

The Safety Analysis Set is the group of subjects who received at least 1 dose of study drug. This is the analyses population used for all safety analyses which will be based on as-treated principle.

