9.7.1.2 Definitions of Analysis Sets

The Full Analysis Set (Intent-to-Treat Analysis [ITT] Population) is the group of all randomized subjects regardless of the treatment actually received. This is the primary analysis population used for all efficacy analyses which will be based on the intent-to-treat principle.

The Per Protocol Analysis Set is the group of those subjects who received at least 1 dose of study drug, had no major protocol deviations and had both baseline and at least 1 postbaseline tumor assessments. Subjects for whom death occurred prior to the first postbaseline tumor assessment will also be included. The per protocol analysis set will be the secondary analysis set for efficacy endpoints.

The Safety Analysis Set is the group of subjects who received at least 1 dose of study drug. This is the analyses population used for all safety analyses which will be based on as-treated principle.

Population Pharmacokinetic (PK) Analysis Set: All the subjects who have received at least 1 dose of study treatment with documented dosing history in the lenvatinib plus everolimus arm (Arm A) or the lenvatinib plus pembrolizumab arm (Arm B), and have measurable plasma levels of lenvatinib, or whole blood levels everolimus.

Pembrolizumab Pharmacokinetic (PK) Analysis Set: All subjects who have received at least 1 dose of study treatment with documented dosing history in the lenvatinib plus pembrolizumab arm (Arm B) and have measurable serum concentrations of pembrolizumab.

The Pharmacodynamic Analysis Set is the group of subjects who received at least 1 dose of study drug and had sufficient pharmacodynamic data to derive at least 1 pharmacodynamic measurement and with documented dosing history.

The QOL Analysis Set will consist of all subjects who have any QOL data.

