#### 5.1.2 Secondary Endpoints

- Objective response rate (ORR), defined as the proportion of subjects who have best overall response (BOR) of CR or PR as determined by IIR using RECIST 1.1. ORR will be calculated for confirmed CR/PR, and for confirmed and unconfirmed CR/PR. Confirmed CR/PR will be primary for ORR analysis.
- Overall survival (OS), defined as the time from the date of randomization to the date of death from any cause. Subjects who are lost to follow-up and those who are alive at the date of data cutoff will be censored at the last date the subject was last known alive, or date of data cutoff, whichever occurs first.
- Safety will be assessed summarizing the incidence of treatment-emergent adverse events (TEAEs) and SAEs together with all other safety parameters.
- Proportion of subjects who discontinue treatment due to toxicity is defined as the proportion of subjects who discontinue study treatment due to treatment-emergent adverse events (TEAEs).
- Time to treatment failure is defined as time from the date of randomization to the date that a subject discontinues study treatment due to TEAEs.
- Health-Related Quality of Life (HRQoL), assessed using the Functional Assessment of Cancer Therapy Kidney Syndrome Index-Disease-Related Symptoms (FKSI-DRS), the European Organization for the Research and Treatment of Cancer (EORTC) QLQ-C30 and the European Quality of Life (EuroQOL) EQ-5D-3L instruments. This analysis will be detailed in a separate SAP for HRQoL.
- PFS on next-line therapy (PFS2), defined as the time from randomization to disease progression on next-line treatment or death from any cause (whichever occurs first).
- Progression-free survival (PFS) by investigator assessment is defined as the time from the date of randomization to the date of first documentation of disease

progression based on the investigator assessment per RECIST v.1.1 or death (whichever occurs first).

- Pembrolizumab PK comparison to historical data. This analysis will be detailed in a separate SAP for PK/PD.
- Model-predicted clearance and AUC for lenvatinib in Arms A and B. This analysis will be detailed in a separate SAP for PK/PD.
- Model-predicted clearance and AUC for everolimus in Arm A. This analysis will be detailed in a separate SAP for PK/PD.

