## 5.2 Study Subjects

### 5.2.1 Definitions of Analysis Sets

The following analysis sets will be defined:

- The Full Analysis Set (Intent-to-Treat Analysis [ITT] Population) is the group of all randomized subjects regardless of the treatment actually received. This is the primary analysis population used for all efficacy analyses which will be based on the intent-to-treat principle.
- The Per Protocol Analysis Set is the subjects who received at least one dose of

any study drug, had no major protocol deviations and had both baseline and at least 1 postbaseline tumor assessments. Subjects who died prior to the first postbaseline tumor assessment will also be included. The per protocol analysis set will be the secondary analysis set for efficacy endpoints.

- The Safety Analysis Set is the group of subjects who received at least one dose of any study drug. This is the analysis population for all safety analyses, which will be based on as-treated principle.
- Population Pharmacokinetic (PK) Analysis Set: All subjects who have received at least one dose of study treatment with documented dosing history in the lenvatinib plus everolimus arm (Arm A) or the lenvatinib plus pembrolizumab arm (Arm B), and have measurable plasma levels of lenvatinib or whole blood levels of everolimus.

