**Table 1 Analysis Sets in Data Analysis**

Data Category	Full	Per Protocol	Safety
Protocol Deviations	•		
Disposition	•		
Demography & Baseline Characteristics	•		
Disease History	•		
Prior & Concomitant Medications	•		
Progression-Free Survival	•	•	
Tumor Response	•	•	
Overall Survival	•	•	
Drug Exposure			•
Adverse Events			•
Deaths			•
Laboratory Tests			•
Vital Signs			•
ECGs			•
Echocardiography			•

- Pembrolizumab PK Analysis Set: All subjects who have received at least one dose of study treatment with documented dosing history in the lenvatinib plus pembrolizumab arm (Arm B) and have measurable serum concentrations of pembrolizumab.

- The Pharmacodynamic Analysis Set is the group of subjects who received at least one dose of study drug and had sufficient pharmacodynamic data to derive at least one pharmacodynamic parameter and with documented dosing history.
- The HRQoL Analysis Set will consist of all subjects who have any HRQoL data.

Table 1 shows each analysis set to be primarily used in each data category but not limited to the specifications in this table.

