#### 5.4.2 Secondary Efficacy Analyses

All analyses of secondary efficacy endpoints will be performed based on Full Analysis Set as the primary analysis set and Per Protocol analysis set as the secondary analysis set.

1. Overall Survival (OS) will be compared between lenvatinib + everolimus (Arm A) and sunitinib alone (Arm C), and between lenvatinib + pembrolizumab (Arm B) and sunitinib alone (Arm C), using the stratified log-rank test with geographic region and MSKCC prognostic groups as strata. The hazard ratio and its 95% CI comparing lenvatinib + everolimus (Arm A) versus sunitinib alone (Arm C) and lenvatinib + pembrolizumab (Arm B) versus sunitinib alone (Arm C) will be estimated by a stratified Cox proportional hazards model with Efron's method for ties, stratified by geographic region and MSKCC prognostic groups. Median OS

and the OS rate at 12, 18, 24 months, and so on (depending on data adequacy) with 2-sided 95% CIs will be calculated using K-M product-limit estimates for each treatment arm and K-M estimates of OS will be plotted over time. Three interim and a final analyses of OS are planned to be performed (SAP [Section 6](#)). Lan-DeMets spending function with Pocock boundary will be used to control alpha levels among the interim and final analysis of OS (SAP [Section 5.3.3](#)). The first two OS interim analyses will be performed at the time of PFS interim and final analysis, corresponding to approximately 45% and 60% of information fractions of OS events. The third OS interim analysis will be performed at approximately 80% information fraction of OS events. The final analysis of OS will be performed when 304 OS events are observed for each comparison.

All events of death will be included, regardless of whether the event occurred while the subject was still taking study drug, or after the subject discontinued study drug. Subjects who were alive at the data cutoff date will be censored at the data cutoff date. Subjects who were lost to follow-up or withdrew consent will be censored at the date the subject was last known to be alive.

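### For overall survival, a never-scanned subject enters the Per Protocol set only by dying, so the secondary OS hazard ratio can be biased in either direction

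*Protocol*

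**What the plan says.** The Protocol synopsis (Statistical Methods, Analysis Sets) limits the Per Protocol set to subjects who took at least one dose, "had no major protocol deviations and had both baseline and at least 1 post-baseline tumor assessments". It then makes one exception: "Subjects for whom death occurred prior to the first post-baseline tumor assessment will also be included". Protocol 9.7.1.2 repeats the exception ("Subjects for whom death occurred prior to the first postbaseline tumor assessment will also be included"), and so does SAP 5.2.1 ("Subjects who died prior to the first postbaseline tumor assessment will also be included"). None of the three places says when the death must occur. SAP 8.1.1 defines early death as death within 121 days of randomization but does not tie that definition to this set.

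SAP 5.4.2 analyses all secondary efficacy endpoints with the "Full Analysis Set as the primary analysis set and Per Protocol analysis set as the secondary analysis set", and OS is the first endpoint it lists. SAP Table 1 marks OS under both the Full and the Per Protocol columns. OS itself is "defined as the time from the date of randomization to the date of death from any cause" (SAP 5.1.2), so it can be observed without any scan. Of the Full Analysis Set the synopsis says: "This is the primary analysis population used for all efficacy analyses which will be based on the intent-to-treat principle".

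**The concern.** A scan condition has a purpose for PFS and response, which are read from scans. For OS it has none, and the death exception turns it into selection on the endpoint. Among never-scanned subjects the set keeps those who die and drops those who live. Each one kept contributes an event, and each one dropped would have contributed event-free follow-up. The arm with more never-scanned subjects therefore looks worse than it is.

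The set is also not fixed over time. OS is analysed four times (Protocol Table 9). Read literally, a never-scanned subject can be outside the set at the first look and inside it at the last, solely because of dying in between.

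Such subjects can arise without a deviation. Scans start at week 8. After treatment stops they end once a new anticancer therapy begins, while survival follow-up continues every 12 weeks (Protocol 9.1.2.2). What is at stake is how far the Per Protocol OS estimate can be trusted as a check on the main OS result.

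**Working it through.** **1. The plan's own OS design reproduces.** Inputs are from Protocol 9.7.2 and Table 11: 304 deaths, two-sided alpha 0.045, medians 54.1 and 37.9 months (37.9/54.1 = 0.70), looks at 137, 182, 243 and 304 deaths, Lan-DeMets Pocock-type spending.
- Fixed design: sqrt(304)/2 × |ln 0.70| − 2.005 = 8.718 × 0.3567 − 2.005 = 1.105, which is 86.5% power.
- Group-sequential: 80.1% power (stated 80%), with nominal p-values 0.0258, 0.0151, 0.0157, 0.0157 (stated 0.0258, 0.0152, 0.0158, 0.0158).

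No stated figure is in dispute. This step only confirms the inputs used below.

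**2. The rule applied to two subjects.** Both are dosed, free of major deviations, have a baseline scan and no later scan, and stay in survival follow-up. One dies in month 20 and is in the set. The other is alive at cutoff and is out. They differ only in the OS outcome.

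**3. Size, by simulation.** Setup: 350 per arm, uniform 34-month accrual, exponential OS at the protocol medians, 3% per year loss, cutoff by number of deaths, unstratified Cox model, 2000 trials per scenario. The share with no post-baseline scan is an assumption (2% to 8% per arm), and scan status is unrelated to survival. The nearest figure in the documents is the 5% dropout trigger in Protocol 9.1. Each trial is analysed on all subjects and on the set as worded. The ratio is the Per Protocol HR divided by the all-subjects HR.

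| Never-scanned, test/control | True HR | Ratio at 137 deaths | Ratio at 304 deaths | True HR × ratio at 304 |
|---|---|---|---|---|
| 2% / 2% | 0.70 | 1.001 | 1.001 | 0.701 |
| 5% / 5% | 0.70 | 1.002 | 1.004 | 0.703 |
| 5% / 5% | 1.00 | 1.000 | 1.000 | 1.000 |
| 2% / 5% | 0.70 | 0.976 | 0.981 | 0.687 |
| 5% / 2% | 0.70 | 1.029 | 1.025 | 0.718 |
| 2% / 8% | 0.70 | 0.950 | 0.960 | 0.672 |
| 8% / 2% | 0.70 | 1.058 | 1.050 | 0.735 |
| 2% / 8% | 1.00 | 0.949 | 0.956 | 0.956 |
| 8% / 2% | 1.00 | 1.053 | 1.046 | 1.046 |

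At 2%/8% and 304 deaths, about 350 × 0.08 = 28 control subjects are never scanned. Some 13.6 are dead and kept, and 28.0 − 13.6 = 14.4 are alive or censored and dropped. In the test arm 2.7 of 7.0 are kept. Relative to sampling error: ln 0.960 = −0.041, the standard error of the log HR is about 2/sqrt(304) = 0.115, and 0.041/0.115 = 0.36 standard errors.

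**4. What shrinks it.** Keep 2%/8% and true HR 0.70 at 304 deaths, and let a fraction of never-scanned subjects leave survival follow-up within 2 months (again an assumption):

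| Fraction leaving | Shift in log HR | 0.70 reads as |
|---|---|---|
| 0% | −0.041 | 0.672 |
| 50% | −0.022 | 0.685 |
| 80% | −0.010 | 0.693 |
| 100% | −0.002 | 0.699 |

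If only deaths within 2 months of randomization qualify for the exception, the HR changes by about 0.003 or less.

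**The case against.** The case against giving this weight is strong on size.

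- **No decision rests on the estimate.** The Full Analysis Set is primary for every efficacy endpoint. This stands.
- **The group may be small and carry little follow-up.** Subjects who stop without progression keep 8-weekly scans until progression or new therapy. Protocol Table 7, footnote u, calls for an off-treatment scan when more than 4 weeks have passed since the last one and the subject will not continue follow-up scans. Many living never-scanned subjects would then be early withdrawals or losses, censored early for OS, and dropping them costs little. This stands in large part. It does not cover subjects who switch therapy early, miss that scan and remain in survival follow-up.
- **Major-deviation criteria are still to be set before database lock** (SAP 5.2.3) and could cover missing scans. That is possible but not stated.
- **The clause may mean death before the first scan was due.** That is a fair reading and makes the shift negligible. But the text does not say so, and someone programming it literally would build the outcome-dependent set.

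A reader might infer that the open-label design pushes the bias in favour of the combinations. The documents do not support that. They give no never-scanned shares, the reversed imbalance moves the HR the other way, and a subject who refuses the assigned arm and takes no dose fails the dosing condition whether alive or dead.

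**Conclusion.** The definition makes Per Protocol membership depend on the OS outcome, and the Per Protocol OS hazard ratio can be biased as a result. Whether it is biased, and in which direction, depends on never-scanned shares that the documents do not give. With equal shares the shift is 0.4% or less. With 2% against 5% to 8% it is roughly 2% to 6%, either way. The move from 0.70 to about 0.67, or to about 0.735, is an upper end. It assumes the widest imbalance considered, scan status unrelated to survival, full survival follow-up of never-scanned subjects, and the literal reading of the clause.

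Two stronger inferences are tempting and do not hold. The alpha-controlled OS test is not compromised, because it uses the Full Analysis Set. The Per Protocol PFS analysis does not need the same repair: a living subject with no post-baseline scan is censored at randomization (SAP Table 4, No. 1) and adds nothing whether in or out. Severity is minor.

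**What to change.** In SAP 5.2.1, with matching text in the Protocol synopsis and 9.7.1.2 at the next amendment, define the Per Protocol set for OS as subjects with at least one dose of study drug and no major protocol deviation, with no condition on post-baseline scans or on death. In the simulation this brings the Per Protocol HR back to the all-subjects HR (ratio 1.000).

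Leave the Per Protocol definition for PFS and tumor response as it is. Adding a short day limit to the death clause there would gain little and would sit badly with the SAP's own 121-day rule for early death (SAP 5.4.1 and 8.1.1). Deleting the death exception is not a remedy either: it would make survival to the first scan a condition of entry and exclude early deaths.

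The cost is a sentence or two in the SAP, the protocol wording, one extra population flag, and slightly different Per Protocol counts for OS and PFS.

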4 LIST OF ABBREVIATIONS AND DEFINITIONS OF TERMS

Abbreviation	Term
AEs	adverse events
AJCC	American Joint Committee on Cancer
ALP	alkaline phosphatase
ALT	alanine aminotransferase
ANC	absolute neutrophil count
AST	aspartate aminotransferase
β-hCG	beta-human chorionic gonadotropin
BMI	body mass index
BP	blood pressure
CBR	clinical benefit rate (CR + PR + durable SD ≥ 23 weeks)
CI	confidence interval
CMH	Cochran-Mantel-Haenszel
CPK	creatinine phosphokinase
CR	complete response
CRA	clinical research associate
CRF	case report form
CRO	contract research organization
CT	computed tomography
CTCAE	Common Terminology Criteria for Adverse Events
CV	curriculum vitae
CVA	cerebrovascular accident
CYP	cytochrome P
DCR	disease control rate
DLT	dose-limiting toxicity
DMC	data monitoring committee
DOR	duration of response
durable SD	durable stable disease
ECG	electrocardiogram
EORTC	European Organization for the Research and Treatment of Cancer

Abbreviation	Term
EuroQOL	European Quality of Life
¹⁸ F-NaF	¹⁸ F-sodium fluoride
FDA	Food and Drug Administration
FGF	fibroblast growth factor
FKSI-DRS	Functional Assessment of Cancer Therapy Kidney Symptom Index-Disease-Related Symptoms
FWER	familywise error rate
GCP	Good Clinical Practice
GI	gastrointestinal
HR	hazard ratio; heart rate
HRQoL	Health-Related Quality of Life
ICF	informed consent form
ICH	International Council for Harmonisation of Technical Requirements for Pharmaceuticals for Human Use
ICL	imaging core laboratory
IEC	Independent Ethics Committee
IIR	independent imaging review
INR	international normalized ratio
IRB	Institutional Review Board
ITT	intent-to-treat data set
IV	intravenous
IxRS	interactive voice and web response system
K-M	Kaplan-Meier
KPS	Karnofsky Performance Status
LLN	lower limit of normal
LLT	lower level term
LMWH	low molecular-weight heparin
LVEF	left ventricular ejection fraction
mAbs	monoclonal antibodies
MedDRA	Medical Dictionary for Regulatory Activities
MRI	magnetic resonance imaging

Abbreviation	Term
MSKCC	Memorial Sloan-Kettering Cancer Center
MTD	maximum tolerated dose
mTOR	mammalian target of rapamycin
MUGA	multiple-gated acquisition
NAb	neutralizing antibody(ies)
NCCN	National Comprehensive Cancer Network
NSAID	non-steroidal antiinflammatory drug
NYHA	New York Heart Association
ORR	objective response rate
P-gp	CYP3A4/P-glycoprotein
PR	partial response
pRBC	packed red blood cells
PRES/RPLS	posterior reversible encephalopathy syndrome/reversible posterior leukoencephalopathy syndrome
OS	overall survival
PD	progressive disease; pharmacodynamics
PFS	progression-free survival
PFS2	progression-free survival during next-line therapy
PG	Pharmacogenomics
PI	principal investigator
PR	partial response
PK	pharmacokinetics
PT	preferred term
Q1	first quartile
Q3	third quartile
Q3W	every 3 weeks
QD	once daily
RBC	red blood cell
RCC	renal cell carcinoma
RECIST	Response Evaluation Criteria in Solid Tumors
RTK	receptor tyrosine kinase

Abbreviation	Term
SAE	serious adverse event
SAP	statistical analysis plan
SD	stable disease
SI	Système International
SOC	system organ class
SOPs	standard operating procedures
TAM	tumor associated macrophage
TEAEs	treatment-emergent adverse events
TEMAV	treatment-emergent markedly abnormal laboratory values
ULN	upper limit of normal
VEGF	vascular endothelial growth factor
VEGFR	vascular endothelial growth factor receptor
WBRT	whole brain radiation therapy
WHO DD	World Health Organization Drug Dictionary

5 ETHICS

5.1 Institutional Review Boards/Independent Ethics Committees

The protocol, informed consent form (ICF), and appropriate related documents must be reviewed and approved by an Institutional Review Board (IRB) or Independent Ethics Committee (IEC) constituted and functioning in accordance with ICH E6 (Good Clinical Practice), Section 3, and any local regulations. Any protocol amendment or revision to the ICF will be resubmitted to the IRB/IEC for review and approval, except for changes involving only logistical or administrative aspects of the study (eg, change in CRA[s], change of telephone number[s]). Documentation of IRB/IEC compliance with the ICH E6 and any local regulations regarding constitution and review conduct will be provided to the sponsor.

A signed letter of study approval from the IRB/IEC chairman must be sent to the principal investigator (or if regionally required, the head of the medical institution) with a copy to the sponsor before study start and the release of any study drug to the site by the sponsor or its designee (ICH E6, Section 4.4). If the IRB/IEC decides to suspend or terminate the study, the investigator (or if regionally required, the head of the medical institution) will immediately send the notice of study suspension or termination by the IRB/IEC to the sponsor.

Study progress is to be reported to IRB/IECs annually (or as required) by the investigator or sponsor, depending on local regulatory obligations. If the investigator is required to report to the IRB/IEC, he/she will forward a copy to the sponsor at the time of each periodic report. The investigator(s) or the sponsor will submit, depending on local regulations, periodic reports and inform the IRB/IEC (or if regionally required, the investigator and the relevant IRB via the head of the medical institution) of any reportable adverse events (AEs) per ICH guidelines and local IRB/IEC standards of practice. Upon completion of the study, the investigator will provide the IRB/IEC with a brief report of the outcome of the study, if required.

At the end of the study, the sponsor should notify the IRB/IEC and Competent Authority (CA) within 90 days. The definition of the end of the study is the date of the data cutoff for the final analysis of overall survival or last subject/last visit, including discontinuation from the study for any reason, whichever occurs later. The sponsor should also provide the IRB/IEC with a summary of the study's outcome.

In the case of early termination/temporary halt of the study, the investigator should notify the IRB/IEC and CA within 15 calendar days, and a detailed written explanation of the reasons for the termination/halt should be given.

